outcomes over the course of the pregnancy while diabetes control is managed per usual care (Group 1 for women using a non-Dexcom CGM such as Medtronic Enlite CGM or Group 3 for no CGM use). A PRA will maintain an active list of individuals and will update the list continuously as women are assigned into groups. All subjects will have similar clinical visits throughout the pregnancy.

Subjects stratified to Group 2, CGM use with Share™, will be asked to designate followers who will be able to view glucose trends and receive alerts for high or low sensor glucose values on an iPhone, iPad, iPod touch, and/or other compatible device. While multiple followers are allowed, one will be the main follower and will be invited to sign informed consent at the screening visit or within the first two months of each subject's study participation. Subjects stratified into Groups 1 and 3 will be asked to designate a main follower who may be aware of a subject's extreme glucose values (lows or highs) through contact with her and who may intervene on her behalf in such cases and will be invited to sign informed consent at the screening visit or within the first two months of each subject's study participation.

What are the treatment groups?

There will be three 'open-label' treatment arms consisting of routine care in the Pregnancy and Women's Health clinic at the BDC (no CGM use), an intervention arm using the Dexcom G4 or G5 Platinum® CGM system during pregnancy, and an additional treatment arm using the Dexcom G4 or G5 Platinum® CGM system with Share™ remote monitoring capabilities during pregnancy. As this is a non-randomized study and most women will opt to be in the Dexcom alone or Dexcom Share groups, we will include pregnant no CGM users identified through a retrospective chart review into the no CGM arm of the study.

How many subjects per treatment arm?

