A total of up to 40 pregnant women will be prospectively recruited into the study. As this is an 'open-label' study whose group stratification is based on subject characteristics (willingness to wear CGM, subject possession of iPhone, iPad, or iPod touch, follower possession of iPhone, iPad, or iPod touch), we cannot predict the number of subjects per treatment arm. Based on our current pregnant population's willingness to use CGM and device usage, we anticipate that 10 subjects will be in Group 1, 20 subjects in Group 2, and 10 subjects in Group 3. We will include up to 30 additional women in Group 3 identified through a retrospective chart review who were pregnant around the time of study enrollment and before the study began.

In addition, there will one main follower for each prospectively enrolled pregnant subject (up to 40 adults) who will be asked questions once per month about knowledge of the subject's glucose trends and interventions that s/he may have done on her behalf over the last month.

What is the schedule of events for the treatment groups?

After screening, when pregnancy is confirmed subjects will be stratified to Group 1, 2, or 3. Subjects in all groups will have similar study/clinic visits for data acquisition at the screening, pregnancy visits (which occur a minimum of monthly throughout gestation), and post-partum clinic visit. All subjects will be required to test blood glucoses at least 7 times a day throughout pregnancy. All subjects will be asked to log the SMBG values 7 times a day with insulin doses for meals for 1 week every trimester of the pregnancy.

Subjects stratified to CGM wear will be provided with a Dexcom G4 CGM, transmitter, and sensors (4 per month). Subjects stratified to CGM wear who want to use their personal Dexcom G5 devices will be asked to provide Dexcom mobile usernames (if they use G5 with an iPhone) and will be provided with sensors (4

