per month). Subjects already using a Dexcom G4 or G5 CGM will be provided only with the sensors. Replacement transmitters will be provided on an as needed basis during the study. A designated CDE or nurse will train each subject in the use of CGM at Visit 2, including how to use the sensor data (rate of change of glucose, to cross-check with fingerstick blood glucose as per FDA label before action is taken). Subjects in Group 2 will be additionally instructed on how to use the Platinum System with Share™ and will set up contact lists with family and friends at that visit. Subjects will be asked to wear the CGM for the duration of the pregnancy and to change sensor sites every 7 days. All subjects will be encouraged to check the blood glucose level (SMBG) before taking action on the CGM glucose values (as per the FDA label). Subjects in Groups 1 through 3 will be asked to designate a main follower who is willing to sign informed consent and fill out a questionnaire once a month.

Subjects will be asked to return to clinic a minimum of once per month for pregnancy care with a BDC provider and to receive the next month's sensors from a designated PRA. There are women whom we ask to return to clinic based on their clinical needs every week or every 2 weeks for pregnancy care who will be allowed to pick up sensors on a biweekly basis rather than monthly, if preferred. If a patient misses an appointment and needs to pick up sensors, she will be asked to reschedule her pregnancy visit and will be allowed to pick up sensors from the PRA for one more month. All subjects will be allowed to keep the devices used in the study upon completion.

The final study visit will occur in conjunction with the post-partum visit.

What is the schedule of events for the follower group?

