All subjects will have routine post-partum clinical care between 4 and 6 weeks post-partum. However, a post-partum visit up to 12 weeks post-partum will be accepted as a final study visit. Data on all subjects for medications, vital signs, height/weight, insulin doses, SMBG values, glucometer downloads, insulin pump downloads (if applicable), and CGM downloads (if applicable) will be collected. All subjects will be asked to

collect a 7-point profile for SMBG measurements (blood glucose measurements before meals, 2 hours after meals, and at bedtime) along with meal insulin dosing for 1 week in the post-partum period (see SMBG Questionnaire). A1C will be measured. Subjects will be asked about updated concomitant drugs and any AEs that may have occurred. Subjects in Groups 1 and 2 may have had a Dexcom G4 Platinum CGM® for personal use prior to study participation and may thereafter still wear the device after labor and delivery. In such cases, CGM downloads will be included in study data. On source documents, we will record how often subjects required an intervention for low or high glucose values within the previous month, and the nature of the interventions. Subjects will be administered a questionnaire inquiring about the labor and delivery process, maternal and fetal complications before and after delivery, baby's anthropometrics at birth (weight and length), baby's current age, breastfeeding, and other measures (see *BDC Pregnancy CGM Post-Partum Questionnaire* for details). If the pregnancy ended early (for example, spontaneous abortion or stillbirth) or resulted in fetal or neonatal death (for example, stillbirth) we will obtain data about these outcomes. Each subject will be given a hypoglycemic fear questionnaire. Followers will be asked to fill out their last *Follower Questionnaire* during the post-partum period.

Control Arm:

As outlined in the proposal, the subjects prospectively enrolled in this arm (Group 3) will receive the same care as in the intervention arms (Groups 1 and 2) with the exception of not having access to the Dexcom G4 Platinum CGM® with or without Share™ technology.

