CGM: Continuous glucose monitoring is an FDA approved technology that offers a unique and practical way of identifying and differentiating clinical benefits of intensive diabetes care. The American Diabetes Association currently recommends CGM use during pregnancy for high-risk individuals (2). We currently have hundreds of patients, which include many pregnant patients, in the Adult Clinic at The BDC using CGM on a regular basis as part of usual medical management of their diabetes. Subjects may experience pain at the site of sensor insertion. The adhesive pads for the sensor may cause skin erythema for 1 to 2 days or more. An allergic reaction to 1 or more parts of CGM devices may occur which can be mild, moderate, or severe (rare). In rare cases, an infection at the sensor site may occur. In rare cases, the sensor or needle may break inside the body and would require a minor surgical procedure to remove it.

Data Collection Tools:

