The primary endpoints are glucose variability and changes detected by hypoglycemic fear survey. We will measure indices of glucose variability (mean glucose \pm SD, % of glucose within/above/below target ranges, J Index, High Blood Glucose Index [HBGI], Low Blood Glucose Index [LBGI], Mean Amplitude of Glycemic Excursions [MAGE], CONGA_n) throughout pregnancy using the SMBG 7-point profiles for one week taken once per trimester. Hypoglycemic fear survey results will be assessed once monthly over the pregnancy. We will compare outcomes within individuals over time and between individuals of the different study arms. We will test whether outcomes differ between women using Dexcom alone and women using Dexcom with Share™ using interaction terms, and will stratify analyses if differences by group are greater than 10 mg/dL in mean glucose levels are detected. Since SMBG logs will be taken at multiple time points over the pregnancy and since CGMs will be worn continuously for the duration of each pregnancy, linear mixed models will be used to assess changes in outcome measures (GV, time spent in target below or above target) over time in each trimester of pregnancy. We will use linear mixed models to assess changes in the hypoglycemic fear survey in each month of the pregnancy. Secondary endpoints include A1C differences among study arms. Improvement in glycemic variability parameters with a possible reduction of A1C by 0.3%, measured as the difference of the mean A1C laboratory values of the arms of the study between baseline (0-3 months, first trimester), second trimester (3-6 months), and third trimester (6 to 9 months). Mixed models account for missing data, allow for an unstructured covariance matrix for repeated measures, and account for inter-subjects correlation of measurements. Secondary outcomes will be used

in the same mixed models. Differences in frequency of low alert glucose rates, high alert glucose rates, and interventions for low or high glucose values among the followers for each study arm will be analyzed with student t-tests. A p-value < 0.05 will be considered significant, and we will perform statistical analyses with SAS software (version 9.3, SAS Institute, Cary NC).

Publication Strategy:

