Appendix B

Baseline Participant Questionnaire

Subject ID: _____ Study Visit: (dd/mmm/yyyy) : _____ / _____ / _____

DEMOGRAPHIC INFORMATION

Date of Birth _____
(dd/mmm/yyyy)

Ethnicity

- Asian/Oriental
- African American
- Caucasian
- Hispanic or Latino
- Other

If other, specify _____

Education

- Grade school
- High School/GED
- Some College
- Associates degree
- Bachelor's Degree
- Master's degree
- Other

If other, specify _____

Marital Status

- Single
- Married
- Widowed
- Other

If other, specify _____

DIABETES HISTORY

Duration of Diabetes: _____

Immediate family history of diabetes? Yes No

Method of Insulin delivery:

- MDI
- Pump Therapy
- VGO Insulin Therapy

Type and Average Dose of Insulin Used:

Basal: _____ Dose _____

Bolus: _____ Dose _____

Other Diabetes medications? _____

If yes, specify _____

CGM Use: Current CGM user If yes, duration of previous use _____
 Past CGM user
 Never used CGM

DIABETIC COMPLICATIONS

Diabetic Retinopathy? Yes No Unknown

Diabetic sensory or motor neuropathy? Yes No Unknown

Diabetic autonomic neuropathy? Yes No Unknown

Diabetic nephropathy? (including micro-albuminuria) Yes No Unknown

If yes, please specify the most recent event diagnosed at the time of patient inclusion:

Impaired renal function (estimated GFR by MDRD below 60mL/min)

Micro-albuminuria (30-299mcg per mg creatinine)

Overt proteinuria (equal to or above 300 mcg per mg creatinine)

High Cholesterol? Yes No Unknown

High Blood Pressure? Yes No Unknown

PRE-EXISTING CONDITIONS

Does the subject have any pre-existing conditions? Yes No

If yes, list below

CONCOMITANT THERAPY

Is the subject taking any medications other than insulin? Yes No If yes, list below

PREVIOUS OBSTETRIC HISTORY

Past pregnancy? Yes No
If no, skip to next section.

Fill out information for each pregnancy. If there are more than 4 pregnancies, continue on another sheet.

First Pregnancy

Outcome Date _____
(dd/mmm/yyyy)

Delivery type:

Vaginal 	If yes: Spontaneous 	Induced 	Breech 	Vacuum 	Forceps 
VBAC 	If yes: Spontaneous 	Induced 			
Cesarean Section 	If yes: Low Transverse 	Low Vertical 	Classical 	Unspecified 	

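### Women already using CGM enter Groups 1 and 2 and the SAP pools them with new starters, so within-person change, most clearly in the primary fear survey, is diluted as an estimate of starting CGM

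*Combined protocol and SAP*

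**What the plan says.** The protocol's schedule of events for the treatment groups provides for entrants who already wear the device: "Subjects already using a Dexcom G4 or G5 CGM will be provided only with the sensors". The same section lets a woman use her own G5 in the study. The Visit 14 description says the same of the earlier model: "Subjects in Groups 1 and 2 may have had a Dexcom G4 Platinum CGM® for personal use prior to study participation". Under recruitment, women who decline Dexcom are placed as follows: "Group 1 for women using a non-Dexcom CGM such as Medtronic Enlite CGM or Group 3 for no CGM use". Such entrants need not be rare at this centre, since the risk section states: "We currently have hundreds of patients, which include many pregnant patients, in the Adult Clinic at The BDC using CGM on a regular basis". The inclusion and exclusion criteria have no rule on prior CGM or Share use, and no run-in or washout is described.

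The history is collected. Appendix B has the entry "Current CGM user If yes, duration of previous use", beside options for past users and women who have never used CGM. It has no item on Share. Table 1 places the first fear survey at Visit 2, the visit at which a new starter's first sensor is inserted.

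The Statistical Analysis Plan names glucose variability and change in the fear survey as primary endpoints, and says: "We will compare outcomes within individuals over time and between individuals of the different study arms". Linear mixed models are to assess change by trimester, or by month for the fear survey. The only interaction named is Dexcom alone against Dexcom with Share. The only trigger for stratifying is a group difference of more than 10 mg/dL in mean glucose. CGM status at entry is not a covariate, stratum, subgroup or sensitivity analysis.

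**The concern.** A woman who arrives wearing a sensor moved from no CGM to CGM before her first study measurement. Her change from Visit 2 cannot show what starting CGM does. Pooling her with a woman who starts at Visit 2 averages two different quantities, and the proportions of the mix are not planned, modelled or reported.

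The fear survey is the most exposed endpoint, because change in it is a primary endpoint and its first administration is at Visit 2. The Group 1 versus Group 2 contrast is exposed in another way. Allocation follows device ownership and CGM brand: users of other brands go to Group 1, while an iPhone owner with a personal G5 goes to Group 2 if her follower also has a compatible device. Type and length of CGM experience may therefore differ between the two groups. The section on the study's weakness says the pilot is meant to inform a much larger trial, so a blended estimate of change would carry forward into its planning.

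**Working it through.** **1. The plan's own figures.** 40 recruited × 0.20 = 8 drop-outs, and 40 − 8 = 32 completers, as stated. The anticipated groups are 10 + 20 + 10 = 40, so Groups 1 and 2 hold 30 women. If loss is even across groups (assumed), completers are 8 + 16 = 24 in the CGM groups and 8 in prospective Group 3. The up to 30 retrospective controls complete no fear survey, so fear contrasts with Group 3 rest on prospective women only.

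**2. Which first measurement is already on CGM.**

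| Endpoint | First value used | Continuing user | New starter |
|---|---|---|---|
| Fear survey | Visit 2 (Table 1) | On CGM | At CGM start |
| A1C | First trimester (SAP) | On CGM | Before or after CGM start |
| SMBG profile | 8 to 12 weeks (Appendix D) | On CGM | Before or after CGM start |

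The fear survey is the only row in which the two kinds of woman separate cleanly. This assumes that a new starter completes it before she has meaningful wear; the protocol does not give the order of events within Visit 2.

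**3. Dilution of change.** Let p be the proportion of continuing users, δ the change caused by starting CGM, and δc the on-study change CGM still produces in continuing users. Pooled mean change = (1 − p)δ + pδc. If δc = 0, this is (1 − p)δ. The documents give neither p nor δc, so the following is an illustration with p assumed and δc = 0:

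- p = 25%: 0.75δ
- p = 50%: 0.50δ
- p = 75%: 0.25δ

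If δc lies between 0 and δ, the loss is smaller. If a later trial were sized on the diluted effect, its sample size would grow by 1/(1 − p)²: 1/0.75² = 1.78 at p = 25%, and 1/0.50² = 4 at p = 50%.

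**4. Uneven split between Groups 1 and 2.** Suppose Share has no effect, δc = 0, and p is 20% in Group 1 and 60% in Group 2 (assumed). Group 1 shows 0.80δ and Group 2 shows 0.40δ. The gap of 0.40δ comes from prior use alone. With equal p the gap is zero.

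**5. Levels during pregnancy.** In the CGM groups, continuing users and new starters are both meant to be on CGM at every on-study time point. A comparison of levels with Group 3 therefore sets use against non-use, and the factor (1 − p) does not enter. Women who had already adopted CGM may differ in other ways, which is confounding and could act in either direction.

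**6. Form of the model term.** A main effect of entry status shifts the continuing users' curve up or down but leaves one common slope, so the time effect is still the blend in step 3. Only status × time separates the two changes.

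**The case against.** The best defence is that the protocol asks about CGM use against non-use during pregnancy, not about starting CGM. On that question continuing users belong in the CGM groups and no dilution arises. This stands for level comparisons. It does not cover the plan's analysis of change within individuals or a primary endpoint defined as change.

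A second objection is that new starters do not have a clean baseline either. This stands for the SMBG profile and first-trimester A1C, as the table shows, so removing continuing users would not by itself restore an untreated baseline for those endpoints. It does not apply to the Visit 2 fear survey.

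A third is that continuing users may still change on study: they receive sensors every month and are asked to wear them throughout. The protocol's introduction cites a larger A1C reduction with constant than with intermittent wear. This stands, and it means that δc = 0 is only a limiting case.

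A fourth is that restricting the lead analysis to new starters would discard useful women. A continuing CGM user who first takes up Share at Visit 2 has a valid baseline for Share, whereas a new starter in Group 2 begins CGM and Share together. Numbers also fall quickly: at p = 50%, completers not on CGM at entry would be 10 × 0.8 × 0.5 = 4 in Group 1 and 20 × 0.8 × 0.5 = 8 in Group 2. This stands, and it is why the restricted analysis should be a sensitivity analysis.

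**Conclusion.** The concern holds for within-person change and group-by-time contrasts, most clearly for the primary fear-survey change. The plan pools baselines taken on CGM with baselines taken at CGM start and does not use the field that distinguishes them. The size is unknown; the fractions above rest on assumed values of p and on no further change in continuing users.

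Four stronger readings are tempting and the documents do not support them:

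- **All comparisons with Group 3 are diluted.** Level comparisons are not. They may be confounded.
- **The SAP's 0.3% A1C figure shrinks to 0.225, 0.15 or 0.075** (0.3 × 0.75, 0.50, 0.25). That scaling needs assumed proportions and nil on-study change. The SAP also words the 0.3% as a difference between arm means, although the secondary objectives speak of reduction from baseline.
- **Entrants are known to be using Share already.** No passage says so. It is possible because personal G5 use with an iPhone is allowed, and it would go unrecorded.
- **Earlier CGM use affects only the CGM groups.** The retrospective control arm collects pre-conception CGM downloads where they exist, so some Group 3 women may be past users.

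No washout is needed. This is an inexpensive improvement to a non-randomized pilot and does not invalidate it.

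**What to change.** In the Statistical Analysis Plan:

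- Keep the all-subject mixed models as the lead analysis. Add CGM status at entry (current versus not current, from Appendix B) and its interaction with time, including in the Group 1 versus Group 2 contrast.
- Prespecify a sensitivity analysis of change in women not using CGM at entry, and report continuing users separately, with their number in each group.
- For A1C in new starters, take as baseline the most recent value before CGM start, from Visit 1 or 2 or the pre-conception record, in place of any value in the first-trimester window.
- For the Share contrast, keep continuing CGM users who first start Share at Visit 2, and separate only prior Share users.

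In Appendix B, add one yes/no item on prior Share use.

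The cost is SAP wording and one baseline question; CGM history and pre-conception A1C, where available, are already collected. The price is extra model terms and small subgroups among about 30 CGM women, so the added results should be presented as descriptive, with estimates and intervals.

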CGM data will be analyzed for mean blood glucose values, time spent in hyperglycemic (>240, >300mg/dl) and hypoglycemic (<50, <70, <80 mg/dl) ranges and various indices of glycemic variability. Laboratory analysis for A1C will be performed at baseline, monthly thereafter during the pregnancy, and post-partum. Routine blood tests will be performed in all subjects in each trimester (see Table 1).

Primary outcomes will be:

- 1) Glucose variability as measured by glucose excursions from self-monitoring blood glucose (SMBG) data through log books and downloads as well as CGM downloads and various indices [J-index, mean amplitude of glycemic excursion (MAGE), high blood glucose index (HBGI), low blood glucose index (LBGI)] from CGM downloads.
- 2) Changes detected by the hypoglycemia fear questionnaire.

Secondary outcomes will be:

- 1) How CGM alone and CGM with Share™ usage affect A1C compared to no CGM use,
- 2) Progression of diabetes complications (retinopathy, nephropathy),
- 3) Maternal and fetal outcomes (eclampsia/pre-eclampsia, live birth rates, birth weight, neonatal hypoglycemia, and other similar measures).

Introduction:

Among the US population, 29.1 million people (9.3%) have diabetes (1). Pre-existing diabetes has to be managed very carefully throughout pregnancy to optimize maternal and fetal outcomes (2). Among women

with T1DM who are pregnant, the tools that we have to regulate maternal glucose control include multiple daily injections (MDI), continuous subcutaneous insulin infusion therapy (CSII) also known as insulin pump therapy, and for high-risk individuals continuous glucose monitoring (CGM) (2). CGM use in pregnancy has been shown to be safe, to reduce the frequency of severe hypoglycemia, and to improve A1C values (3-6). Sensor-augmented pump therapy with CGM use continuously was shown to lower A1C more than intermittent use in pregnant women with T1DM (7). However, few studies have measured changes in glucose variability that occur with CGM use during pregnancy and no studies have evaluated how tools that allow family and friends (followers) to access glucose trends affect outcomes during pregnancy.

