During this visit, pregnant subjects will receive a physical exam, vitals, medical history, demographics, and concomitant medications. Laboratory tests will be performed to assess for A1C. SMBG values will be downloaded. If applicable CGM units and insulin pumps will be downloaded.

Stratification, Visit 2 (Week 1):

Subjects enrolled in the study from pre-conception will be asked to come to clinic as soon as a home pregnancy test or serum blood test confirms pregnancy, during which time routine clinical care will be provided and subjects will be stratified to 1 of 3 study arms based on subject characteristics. Subjects who did not have a pre-conception counseling visit who come to clinic for routine clinical care before 13 weeks of gestation will combine Visit 1 (screening) with Visit 2 (stratification with CGM start). A urine pregnancy test will be administered to confirm pregnancy. Per routine clinical care, we will screen for diabetic neuropathy on physical exam, thyroid disease (TSH blood draw), and kidney disease (24-hour urine protein with creatinine). These tests will be repeated once each trimester. Also per routine clinical care, women will be asked to get a dilated retinal eye exam each trimester and to provide the BDC with a copy of the provider's report of each exam.

Women stratified to Groups 1 and 2 who own a Dexcom G4 or G5 Platinum CGM® will be given 4 sensors. Women stratified to Groups 1 and 2 who do not own a Dexcom G4 or G5 Platinum CGM® will be given Dexcom G4 CGM units, transmitters, and 4 sensors. They will also receive training in the insertion of sensors and CGM use. A Dexcom G4 Platinum® CGM sensor will be inserted that day and will be worn in 7 day periods throughout the study. Although subjects will be asked to wear the device 7 days/week, satisfactory data capture rate is regarded as 5 days of successful CGM readings. The CGM data will be unblinded (real-time use) such that subjects will be able to view glucose values and trends, as well as receive alerts for low and high sensor glucose values. Women will be asked to check SMBG at least 7 times daily (fasting, before meals, 2 hours after a meals, and at bedtime) for the duration of the study.

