There will also be a control arm of pregnant patients at the BDC identified through a retrospective chart review who were pregnant around the time of study enrollment or before and who did not use a CGM device throughout their pregnancies. The retrospective chart review will collect data on a subject's medical history, diabetes complications, medications, vital signs, height/weight, A1C, insulin doses, glucose meter downloads, insulin pump downloads (if applicable), and CGM downloads (if applicable) for the most immediate pre-conception visit, all pregnancy visits, and the post-partum visit. Subjects identified through the retrospective chart review will not have filled out any of our questionnaires (baseline, hypoglycemic fear, and postpartum questionnaires), nor will they have had followers who filled out questionnaires. They will not be asked to fill out these questionnaires.

Inclusion Criteria:

Subjects that meet the following criteria will be considered for admission to the study:

1. Signed informed consent before any study-related activities
2. Female aged 18 years and older with T1D duration >1 year
3. Pregnancy with confirmation of gestational age 13 weeks or less
4. Willingness to routinely practice at least 3-7 blood glucose measurements per day
5. Using MDI or CSII therapy
6. Any A1C level
7. Ability and willingness to adhere to the protocol including scheduled study visits for the duration of the pregnancy
8. Able to speak, read, and write English

Exclusion Criteria:

Subjects will be excluded from the study if any of the following apply:

1. Unwilling to sign informed consent and participate in the study
2. Female age 17 years or younger
3. T1D duration <1 year
4. Pregnancy in gestational week 14 or higher
5. Extensive skin changes/diseases that inhibit wearing a sensor on normal skin
6. Severe known allergy to adhesives within the last 3 months
7. Any other condition, as determined by the investigator, which could make the subject unsuitable for the trial, impairs the subject's suitability for the trial, or impairs the validity of the informed consent

Risks and Justification of Procedures:

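### Whole meter downloads mix scheduled and event-triggered fingersticks, so SMBG indices that compare arms using chart-review controls' downloads are biased in a direction the documents do not settle

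*Combined protocol and SAP*

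**What the plan says.** Two parts of the document name different SMBG sources for the first primary outcome. The synopsis list of primary outcomes uses "glucose excursions from self-monitoring blood glucose (SMBG) data through log books and downloads as well as CGM downloads". The Statistical Analysis Plan measures the indices (mean and SD, percent within, above and below range, J-index, HBGI, LBGI, MAGE, CONGA) "throughout pregnancy using the SMBG 7-point profiles for one week taken once per trimester". The Appendix D form for those weeks has slots only before and 2 hours after each meal and at bedtime. The SAP then compares outcomes between study arms.

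On when fingersticks are taken, the section on the schedule of events for the treatment groups sets a minimum of seven tests a day. CGM training teaches women "to cross-check with fingerstick blood glucose as per FDA label before action is taken", and the same section adds "All subjects will be encouraged to check the blood glucose level (SMBG) before taking action on the CGM glucose values". Under Stratification, Visit 2, CGM data are unblinded: "subjects will be able to view glucose values and trends, as well as receive alerts for low and high sensor glucose values". Table 1 collects meter downloads at every visit. No rule labels or sets aside unscheduled readings.

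On the controls, about 10 women are expected to join Group 3 prospectively, and up to 30 more come from chart review. The Control Arm section lists glucose meter downloads among the chart data and says these women completed none of the study questionnaires. No 7-point profile is listed for them.

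**The concern.** A fingerstick index is a summary of the moments at which the woman chose to test. If the reason for testing differs by arm, the index differs by arm even with the same underlying glucose. CGM users have a prompt that others lack: a sensor value or alert, followed by a confirming fingerstick, which concentrates extra tests at suspected lows and highs. Women without CGM may have their own extra tests, prompted by symptoms. Chart controls may also have had fewer scheduled tests, which gives any triggered test more weight.

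The SAP's profile weeks avoid most of this for prospective women. They cannot be applied as they stand to the chart-review women, who are most of the control arm. The comparison with them has to use downloads on at least one side, and the plan does not say how the two sources are to be made comparable. The first hypothesis in the synopsis is a lower percentage of values below target with CGM, which is among the measures most affected by triggered testing.

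**Working it through.** The plan states no figure on this point, so there is none to reproduce. All testing rates below are assumptions.

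**Inputs from the document.** Chart-review share of Group 3: 30/(30 + 10) = 75%. Scheduled readings per profile week: 7 × 7 = 49. Scheduled tests: at least 7 a day for prospective women. For chart controls no frequency is given, so 7 and 4 a day are both tried.

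**Hand calculation.** Let 10% of scheduled readings be below 70 mg/dL in every arm.

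- CGM users, 7 scheduled checks plus k alert-confirming checks a day, a share q of them low: (0.7 + kq)/(7 + k). For k = 1, q = 0.3: 1.0/8 = 12.5%. For k = 3, q = 0.5: 2.2/10 = 22%.
- No CGM, no extra checks: 10%.
- No CGM, 7 scheduled plus 0.5 symptom check a day, 80% of them low: (0.7 + 0.4)/7.5 = 14.7%. With 1 symptom check: (0.7 + 0.8)/8 = 18.8%.
- Chart control, 4 scheduled plus 1 symptom check: (0.4 + 0.8)/5 = 24%.

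The CGM range (12.5% to 22%) lies inside the control range (10% to 24%), so the sign depends on unknown rates.

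**Simulation.** Identical true glucose in all arms: lognormal AR(1), median 125 mg/dL, log-SD 0.38, 6000 days. Fixed daily tests are supplemented by a test on entering <70 or >200 mg/dL, with the stated probability.

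| Readings used | % <70 | % >180 | SD | LBGI | HBGI |
|---|---|---|---|---|---|
| True glucose | 6.2 | 17.1 | 53 | 1.5 | 3.9 |
| 7 scheduled only, any arm | 6.3 | 17.2 | 53 | 1.5 | 3.9 |
| CGM download, 25% of lows / 25% of highs confirmed | 12.0 | 24.4 | 57 | 1.9 | 4.7 |
| CGM, 50% / 50% | 16.1 | 29.6 | 60 | 2.2 | 5.2 |
| CGM, 90% / 90% | 20.6 | 35.4 | 62 | 2.5 | 5.8 |
| CGM, 90% / 25% | 25.3 | 20.7 | 58 | 3.1 | 4.0 |
| CGM, 25% / 90% | 9.5 | 40.3 | 59 | 1.5 | 6.6 |
| No CGM, 7 scheduled + 25% / 0% | 13.3 | 15.9 | 54 | 2.1 | 3.6 |
| No CGM, 7 scheduled + 50% / 10% | 18.7 | 18.3 | 56 | 2.6 | 3.8 |
| Chart control, 4 scheduled, no extra | 6.3 | 16.9 | 53 | 1.5 | 3.9 |
| Chart control, 4 scheduled + 50% / 10% | 25.5 | 18.6 | 57 | 3.1 | 3.7 |

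Check of the 50%/50% row, which had 1.15 low and 1.71 high extra tests a day: (7 × 0.0625 + 1.15)/(7 + 1.15 + 1.71) = 1.5875/9.86 = 16.1%.

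**Whole downloads in both arms.** Percent below 70 ranges from 9.5 − 25.5 = −16 points (favouring CGM) to 25.3 − 6.3 = +19 points (against it). Percent above 180 is higher with CGM in every pairing, from 20.7 − 18.6 = 2.1 to 40.3 − 15.9 = 24.4 points. HBGI is also higher with CGM in every pairing, but the smallest gap is negligible. The share above 240 does not follow this pattern: 3.0% to 3.9% in CGM downloads against 3.2% to 4.5% in controls.

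**Profiles in CGM women, whole downloads in chart controls.** Percent below 70 is 6.3 against 6.3 if chart controls never test on symptoms, and 6.3 against 25.5 if they do. That is 0 to 19.2 points in favour of CGM with no true effect.

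**Smaller spread (log-SD 0.30, true 2.6% below 70 and 11.4% above 180).** CGM downloads with equal confirmation of 25% to 90% give 6.1% to 12.2% below 70 and 17.0% to 27.7% above 180. Symptom-testing controls (50% / 10%) give 9.8% (7 a day) and 14.1% (4 a day) below 70. The pattern is the same.

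**After restriction to scheduled readings.** 6.3% below 70, SD 53, HBGI 3.9, against true values of 6.2%, 53 and 3.9.

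**The case against.** The strongest objection is that the SAP is the operative analysis text and already uses fixed-time profiles, on a form with no place for an alert-triggered reading. No sentence says that whole downloads will feed the between-arm indices; the synopsis only lists downloads as a source. For comparisons among prospective women this stands, and the exposure there is small once the synopsis is brought into line. It does not answer the chart-review comparison, where no profile is listed.

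A reader might infer that the bias necessarily runs against CGM, and that the 10% to 12.5–22% step in the hand calculation (a relative rise of 25% to 120%) measures it. The documents do not support that. The step requires women without CGM to make no symptom-driven checks, every confirming check to be additional to a scheduled one, and a known share of alert checks to be truly below 70. The documents give none of these, and the Visit 2 text individualises the alert thresholds. Confirmation is also only encouraged in the quoted sentence, so its extent is unknown.

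It can also be said that this is a non-randomized pilot without formal power. That limits what any comparison can show, but the SAP still tests at p < 0.05, and this bias can be reduced with data already collected.

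Finally, a time-window filter is imperfect. The chart-review list includes no meal times, and a triggered check may fall inside a window. This is accepted and affects how the rule should be written.

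**Conclusion.** The concern holds as a gap in source specification that should be closed before analysis. The synopsis and the SAP name different SMBG sources, and no rule makes the chart controls' downloads comparable with the prospective women's readings. Whole downloads compared between arms, or profiles compared with whole downloads, give biased indices even when true glucose is the same.

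The size and direction are not determined by the documents. Under the assumptions tried, the artefact in percent below 70 runs from about 16 points in favour of CGM to about 19 points against it when both arms use whole downloads, and from 0 to about 19 points in favour when profiles are set against downloads. With whole downloads in both arms, the share above 180 and HBGI ran against CGM throughout; the share above 240 did not. These figures rest on an assumed glucose distribution and assumed trigger probabilities. They show that the bias can be large, not how large it will be. Neither a bias uniformly against CGM nor a defect in the profile-based comparison among prospective women is established.

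**What to change.** Reconcile the synopsis with the SAP so that every between-arm SMBG index uses scheduled time points only.

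- Among prospective women, use the Appendix D profile weeks.
- For any comparison that includes chart controls, take readings from the meter downloads in all arms by one pre-specified rule that ignores the glucose value. An example is the reading nearest the centre of each fixed clock-time window. Clock time is needed because meal times are not among the listed chart data. This assumes that downloads carry time stamps.
- Report tests per day by arm, so that differences in testing are visible.
- Keep whole-download results as descriptive or sensitivity analyses.

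Prospective women have both a log and a download for the profile weeks, so agreement between the two can be reported as a check on the window rule.

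The cost is SAP wording and a filter on data already held. Visits, data collection and testing instructions are unchanged. The downsides are fewer readings per woman and less precise indices, especially where chart controls have empty windows; only approximate post-meal windows for those women; and some triggered readings still falling inside a window. The simulated removal of the artefact applies to exact scheduled readings, so a window rule should be expected to reduce the bias rather than abolish it.
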